9.9 Recording of Adverse Events and Serious Adverse Events

The Investigator should review all documentation (e.g., hospital progress notes, laboratory, or diagnostic reports) relative to the event being reported. The Investigator will then record all relevant information regarding an AE/SAE into the electronic data system. It is not acceptable for the Investigator to send photocopies of the subjects’ medical records in lieu of completion of the appropriate AE/SAE pages.

The Investigator will attempt to establish a diagnosis of the event based on signs, symptoms, and/or other clinical information. In such cases, the diagnosis should be documented as the AE/SAE and not the individual signs and symptoms.

SAEs will be reported to the IRB within 10 working days or within 24 hours if the event is life-threatening or results in death.

Pregnancies

Subject pregnancy must be reported to the Principal Investigator within 1 working day of knowledge of the event. Any subject that becomes pregnant during the study must be promptly withdrawn from the study. Follow-up information regarding the outcome of the pregnancy and any postnatal sequelae in the infant will be required.

9.10 Intensity of Adverse Events and Serious Adverse Events

The Investigator will make an assessment of intensity for each AE and SAE reported during the study. The assessment will be based on the Investigator's clinical judgment. The intensity of each AE and SAE should be assigned to one of the following categories:

| | |
|-------------------|--|
| Mild: | An event that is easily tolerated by the subject, causing minimal discomfort and not interfering with everyday activities. |
| Moderate: | An event that is sufficiently discomforting to interfere with normal everyday activities. |
| Severe: | An event that prevents normal everyday activities. |
| Life-threatening: | Immediate risk of death. |

An AE that is assessed as severe should not be confused with an SAE. Severity is a category utilized for rating the intensity of an event; and both AEs and SAEs can be assessed as severe. An event is described as 'serious' when it meets one of the pre-defined outcomes as described in Section 8.6, "Definition of Serious."

9.11 Causality of Adverse Events and Serious Adverse Events

The Investigator is obligated to assess the causality between study therapy and the occurrence of each AE/SAE. The Investigator will use clinical judgment to determine if there is a reasonable possibility that the biological action of the study therapy was responsible for AE/SAE being reported. Alternative causes such as natural history of the underlying diseases, concomitant therapy, other risk factors, and the temporal relationship of the event to the study therapy will be considered and investigated. The Investigator will also consult the Clinical Investigator's Brochure and/or Product Information, for marketed products, in the determination of his/her assessment.

The Investigator will use the following questions when assessing causality of an adverse event to study therapy.

Is there a reasonable possibility that the study therapy caused the event? Reasonable possibility implies that there is evidence that the event was caused by the study product. An affirmative answer designates the event as a suspected adverse reaction.

There may be situations when an SAE has occurred and the Investigator has minimal information to include in the initial report. However, it is very important that the Investigator always makes an assessment of causality.

The relationship between AEs and the study exposure will be classified by the investigator as:

- None: No relationship. Related to other known etiologies, conditions, or exposures.
- Unlikely: Current knowledge suggests that a relationship is unlikely.
- Possible: A plausible temporal sequence or response pattern exists but the AE may be related to other known etiologies, conditions, or exposures.
- Probable: A plausible temporal sequence or response pattern exists and the AE cannot be related to other known etiologies, conditions, or exposures.
- Definite: A plausible temporal sequence or response pattern exists and the AE can be confirmed by re-challenge or with other supporting data.

9.12 Follow-Up of Adverse Events and Serious Adverse Events

After the initial AE/SAE report, the Investigator is required to proactively follow each subject and provide further information on the subject's condition. All AEs and SAEs documented at a previous visit/contact that are designated as ongoing will be reviewed at subsequent visits/contacts.

Adverse events and SAEs will be followed until resolution, until no further changes in the event are expected (i.e. the point at which a subject experiencing a critical adverse event is treated successfully and stabilized even though they may continue to experience lingering sequelae that may never resolve), until the subject is lost to follow-up, or until it is agreed that further follow-up of the event is not warranted (e.g. non-serious, study therapy unrelated, mild or moderate adverse events ongoing at a subject's final study visit). If a subject dies during participation in the study or during a recognized follow-up period, the Investigator will provide a copy of any post-mortem findings, including histopathology.

New or updated information will be recorded by modifying the AE forms in the electronic data system

9.13 Timeframes for Submitting SAE Reports

Once an Investigator becomes aware that an SAE has occurred in a study subject, he/she will record the information in the electronic data record within 48 hours. Any fatal or life-threatening event must be reported within 24 hours. If the Investigator does not have all information regarding an SAE, he/she will not wait to receive additional information before

recording the event in the data system and completing as much information known at the time of the submission. The reporting timeframes for any SAE occurring during the study are summarized in Table 2.

TABLE 2
Serious Adverse Event Reporting Requirements

| | Initial Reports | | Follow-Up Reports |
|----------------------|--|--------------------------|-------------------|
| Type of SAE | Fatal or Life-Threatening | Other SAEs | Any SAE |
| Reporting Timeframes | 24 hours | 48 hours | 48 hours |
| Documents Required | 24 hours: Complete as much information in the electronic data system that is known. 48 hours: Fully complete all AE forms | Fully completed AE forms | Updated AE Forms |

9.14 Post-Study Adverse Events and Serious Adverse Events

The Investigator should report any death or SAE occurring at any time after a subject has completed or terminated a clinical trial, when such death or SAE may reasonably be related to the study therapy used in an investigational trial. Investigators are not obligated to actively seek AEs from former study participants.

9.15 Regulatory Aspects of Adverse Event Reporting

The Investigator will promptly report all SAEs within the timeframes specified in Section 8.13. Prompt notification of SAEs by the Investigator is essential so that UMMSM can meet legal obligations and fulfill ethical responsibilities towards the safety of all subjects participating in UMMSM-sponsored investigational trials.

The Investigator will comply with the applicable local regulatory requirements related to reporting of SAEs to his or her Institutional Review Board (IRB) or Independent Ethics Committee (IEC).

This protocol has been filed under an Investigational New Drug (IND) application with the FDA. A given SAE may qualify as an Expedited Safety Report (ESR) if the SAE is both at least possibly attributable to study therapy and unexpected. In this case, all Investigators participating in an IND study will receive an ESR.

The ESRs are prepared according to UMMSM policy and are forwarded to the Investigator as necessary. The purpose of the ESR is to fulfill specific regulatory and Good Clinical Practice (GCP) requirements regarding the product under investigation. Based on previous trials involving intravenous infusion of allogeneic human MSCs, no AEs have been attributed to treatment administration; therefore all AEs will be considered and documented as unexpected AEs.

All AEs occurring at any time during the trial will be collected, documented, and reported by the investigator. For each AE, the investigator will provide the date of onset and resolution, intensity, treatment required, outcome, seriousness, and potential causality with regards to the study exposure.

10. STATISTICAL ANALYSIS

10.1 Determination of Sample Size and Analysis Population

No formal statistical justification was performed to determine sample size in this Phase I/II study. The allocation ratio will be 1:1. All randomized subjects will be included in summaries of baseline characteristics, safety, and efficacy. Reasons for study discontinuation will be tabulated.

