3. STUDY DESIGN

3.1 Description of the Study

Sixteen (16) diabetic subjects with endothelial dysfunction will be scheduled to undergo a peripheral intravenous infusion after meeting all inclusion/exclusion criteria at baseline. The study will consist of a Pilot Phase and Randomized Phase.

PILOT PHASE

To test the safety of allogeneic mesenchymal stem cells therapy for endothelial dysfunction in diabetes subjects administered via peripheral intravenous infusion, a non-randomized, unblinded pilot phase of six subjects will be performed.

Three (3) subjects will be treated with 20 million (20×10^6) allogeneic hMSCs
Three (3) subjects will be treated with 100 million (100×10^6) allogeneic hMSCs.

The three (3) subjects in the low dose group will not be treated less than 5 days apart and will each undergo full evaluation during those five days to show that there are no signs of treatment emergent SAE's before continuing with the treatment of further subjects.

The three (3) subjects in the high dose will not be treated until the three (3) subjects in the low dose have completed their one-month follow-up assessments and safety measures have been reviewed to confirm that there have been no treatment emergent SAE's. In addition, the first three (3) subjects in the high dose group will not be treated less than 5 days apart.

RANDOMIZED PHASE

After the Pilot Phase, the Randomized Phase will begin. Ten (10) diabetic subjects with endothelial dysfunction will be randomized to undergo a peripheral intravenous infusion in a 1:1 ratio after meeting all inclusion/exclusion criteria at baseline.

Five (5) subjects will be treated with 20 million (20×10^6) allogeneic hMSCs Five (5) subjects will be treated with 100 million (100×10^6) allogeneic hMSCs

The Allo-hMSCs will be supplied from an allogeneic human mesenchymal stem cell source manufactured by the University of Miami.

Electronic randomization will be performed by the University of Miami Biostatistics Collaboration and Consulting Core (BCCC) and communicated to cellular laboratory personnel who have no contact with the investigators or subjects. After each infusion, subjects will be monitored for immediate complications.

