4.4 Withdrawal Criteria

Subjects will be informed that they have the right to withdraw from the study at any time and for any reason without prejudice to future or continued medical care. Subjects must be withdrawn for the following reasons:

- Subject's request.
- Subject is unable or unwilling to comply with the protocol.
- Medical reasons, at the discretion of the investigator.

Reason for withdrawal will be recorded in the subject's case report form. In order to adequately monitor for safety and potential efficacy outcomes, subjects who are withdrawn for any reason after receiving the first infusion should be encouraged to return for all assessments through the end of the study period. All efforts should be made to continue to record safety data and lung function parameters for all withdrawn subjects. Subjects who withdraw for reasons unrelated to the study or study drug (e.g. withdrawal of consent or loss to follow-up) may be replaced if deemed necessary to meet study objectives. Replacement subjects will be assigned unique identification numbers.

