- The proportion of subjects experiencing TE-SAE as defined in Section 2.2.1 will be monitored within 30 days of injection. This guideline is designed to assist the independent DSMB in overseeing the study and indicate boundaries needing discussion by the DSMB. The DSMB may also request additional interim analyses and develop other criteria including provision for monitoring of potential late effects to determine when to intervene in the enrollment or treatment of subjects in the study.
- The stopping guidelines serve as a mechanism for consultation with the DSMB for additional review, and are not formal “stopping rules” that would mandate automatic closure of study enrollment. It is designed to assist the independent

DSMB in overseeing the study. The DSMB may also request additional interim analyses and develop other criteria including provision for monitoring of potential late effects to determine when to intervene in the enrollment or treatment of subjects in the study.

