10.3 Interim Analyses

Interim analyses will be conducted at times coincident with regularly scheduled meetings of the Data and Safety Monitoring Board (DSMB) at approximately six-month intervals. The DSMB Chair will be notified each time an SAE occurs. After all subjects in the low dose have been followed for 30 days, at that time an independent DSMB will review all available data to make an independent recommendation to either keep the specified randomized dose 1:1 or to recommend a dose modification.

Policies of the DSMB will be described in the DSMB Charter, which will be prepared by the DSMB prior to study initiation. The stopping guidelines serve as a trigger for consultation with the DSMB for additional review, and are not formal “stopping rules” that would mandate automatic closure of study enrollment.”

11 Data Safety and Monitoring Board (DSMB)

NHLBI Gene and Cell Therapy Data and Safety Monitoring Board

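### Section 10.1 assigns only randomized subjects to the safety summaries, so the six non-randomized pilot subjects (6 of 16 planned) have no stated place in the primary TE-SAE incidence

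*Combined protocol and SAP*

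**What the plan says.** Section 10.1, whose title includes the analysis population, gives one rule: "All randomized subjects will be included in summaries of baseline characteristics, safety, and efficacy". No other section names a safety, treated or infused set. Section 10.2 tabulates adverse events without saying for whom.

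Section 3.1 sets the total: "Sixteen (16) diabetic subjects with endothelial dysfunction will be scheduled to undergo a peripheral intravenous infusion". It splits that total into two phases. The first is the pilot, where "a non-randomized, unblinded pilot phase of six subjects will be performed", three subjects at each dose, for the stated purpose of testing safety. In the second, "Ten (10) diabetic subjects with endothelial dysfunction will be randomized to undergo a peripheral intravenous infusion in a 1:1 ratio", five at each dose.

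The primary endpoint in Section 2.2.1 is the incidence of TE-SAEs one month after infusion, with no denominator given. Section 9.2.4 monitors the same endpoint without limiting it to a phase: "The proportion of subjects experiencing TE-SAE as defined in Section 2.2.1 will be monitored within 30 days of injection".

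For data collection, Section 9.15 states: "All AEs occurring at any time during the trial will be collected, documented, and reported by the investigator". Section 10.3 has the DSMB Chair notified of each SAE.

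**The concern.** The primary objective is safety, and the primary result is a proportion. The rule that should fix its denominator covers the ten randomized subjects and is silent on the six who were treated first and specifically to test safety. Applied as written, it puts the primary summary on 10 of 16 infused subjects.

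Two things follow. A TE-SAE in the pilot would be known to the DSMB yet could be absent from the reported primary incidence. If the pilot is free of events, the report would carry a wider interval than the collected data support. In addition, the proportion followed under Section 9.2.4 could rest on 16 subjects while the final summary rests on 10, so the two would not be comparable. Because the choice is open, it could be made after the pilot results are known.

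**Working it through.** **Inputs.** Pilot 3 + 3 = 6 and randomized 5 + 5 = 10 (Section 3.1). Two-sided 95% intervals are planned where appropriate (Section 10.2), but no method is named. I assume exact (Clopper-Pearson) intervals. The documents give no expected TE-SAE rate, so the rates in step 4 are assumptions.

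**1. The plan's own count.** 3 + 3 + 5 + 5 = 16, which agrees with Section 3.1. Section 10.1 gives no power calculation to reproduce.

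**2. Share without a stated place.** 6/16 = 37.5% overall and 3/8 = 37.5% at each dose.

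**3. No events.** The exact two-sided 95% upper limit is 1 − 0.025^(1/n):

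| Set | Randomized only | All infused |
|---|---|---|
| Overall | 0/10: 30.8% | 0/16: 20.6% |
| Per dose | 0/5: 52.2% | 0/8: 36.9% |

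**4. Chance that the pilot contains an event.** P(at least one) = 1 − (1 − p)^m, with m = 6 for the whole pilot and m = 3 for the high-dose pilot subjects:

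| Assumed rate p | m = 6 | m = 3 |
|---|---|---|
| 5% | 26.5% | 14.3% |
| 10% | 46.9% | 27.1% |
| 20% | 73.8% | 48.8% |

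The m = 3 column is shown because Section 3.1 makes the high-dose pilot depend on there being no TE-SAE in the low-dose pilot. A high-dose pilot event is therefore the more natural route to a pilot event followed by a randomized phase. These are chances that an event occurs, not that it is left out of the report.

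**5. One pilot event, none later, trial continued as planned.**

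- Randomized set: 0/10 = 0% (95% CI 0 to 30.8%).
- All infused: 1/16 = 6.3% (95% CI 0.2 to 30.2%).

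**Limits on the counts.** The figures 16, 10 and 8 hold only if nobody is replaced and the doses stay as planned. Section 4.4 says certain withdrawn subjects "may be replaced if deemed necessary to meet study objectives". Section 10.3 lets the DSMB "either keep the specified randomized dose 1:1 or to recommend a dose modification".

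**The case against.** The strongest reply is that Section 10.1 is inclusive. It guarantees that no randomized subject is dropped and does not contain the word only. Other text leans towards 16. Section 3.1 describes one study of sixteen infused subjects, and Section 2.2.1 counts from infusion, not randomization. Section 6.6 ties the unblinded pilot to the primary safety objective. Section 11.8 asks for all adverse events over the whole study in DSMB reports. On this view pilot events are unlikely to go unreported. This part stands: the pilot subjects are unassigned rather than excluded, and collection and oversight are not at fault. But none of these sections states a denominator, and the one section meant to do so names a different group.

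The second reply concerns weight. No test, threshold or formal stopping rule depends on the denominator. With one pilot event the two upper limits, 30.8% and 30.2%, are practically the same, and with none the ten-subject reading is the more cautious. A pilot TE-SAE might also stop or change the trial before randomization. This is fair, and it keeps the point from being more serious than it is. What still changes is whether the primary result reads as no event or one event, and how precise a clean result appears.

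Third, a mismatch between monitoring and final report is only possible, not shown. Section 11.12 allows the monitoring plan to sit in a separate document, which could settle the monitored denominator. That is correct, but it would not settle the final one.

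**Conclusion.** The concern holds. Following the one stated rule puts the primary safety incidence on 10 of 16 planned infused subjects, and no other text assigns the remaining six (37.5%). In an event-free trial the cost is an exact upper limit of 30.8% instead of 20.6% overall, and 52.2% instead of 36.9% per dose. With a single pilot event, the headline could be 0/10 or 1/16.

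These sizes assume Clopper-Pearson intervals, no replacement and no dose modification. The single-event example also assumes that the trial continued as planned, and the probabilities of a pilot event rest on assumed rates of 5% to 20%. The absence of a stated denominator for the pilot subjects depends on none of these. It should be fixed, since the cost is very small and the endpoint is the primary one.

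**What to change.** In Section 10.1, define two sets.

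1. **Safety set:** every subject in whom an infusion was started, by dose received (planned n = 16, subject to replacement or dose modification). Show it by phase and pooled, with exact 95% confidence intervals. Use it for the primary endpoint, the adverse event tables and the TE-SAE proportion in Section 9.2.4, so that monitoring and final report share one denominator. Under this definition a subject randomized but never infused does not count, and an infused replacement does. An infused subject who is later replaced also stays in.
2. **Randomized set:** the planned ten, for the between-dose efficacy comparison, with pilot efficacy data shown descriptively beside it.

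The cost is two or three sentences in Section 10.1 and a cross-reference in Section 9.2.4. No new data are needed, and treatment and follow-up do not change. The one drawback is that the pooled safety estimate mixes an open-label and a blinded phase, which the by-phase display makes visible.

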10.2 General Statistical Methods

All statistical tests will be performed at an $\alpha=0.05$ level of significance, using two-sided tests. Because this is a Phase I/II study with only exploratory efficacy outcomes, no adjustments will be made for multiple analyses. Continuous variables will be presented by descriptive statistics. Categorical variables will be presented by counts. Two sided 95% confidence intervals will be calculated and presented where appropriate.

Analysis of AEs will include tabulation by frequency, severity, organ system affected, and relationship to study exposure. Lung function data will be summarized descriptively. Subject reported outcome data will be summarized according to the guidelines of each questionnaire.

10.3 Interim Analyses

Interim analyses will be conducted at times coincident with regularly scheduled meetings of the Data and Safety Monitoring Board (DSMB) at approximately six-month intervals. The DSMB Chair will be notified each time an SAE occurs. After all subjects in the low dose have been followed for 30 days, at that time an independent DSMB will review all available data to make an independent recommendation to either keep the specified randomized dose 1:1 or to recommend a dose modification.

Policies of the DSMB will be described in the DSMB Charter, which will be prepared by the DSMB prior to study initiation. The stopping guidelines serve as a trigger for consultation with the DSMB for additional review, and are not formal “stopping rules” that would mandate automatic closure of study enrollment.”

11 Data Safety and Monitoring Board (DSMB)

NHLBI Gene and Cell Therapy Data and Safety Monitoring Board

11.1 INTRODUCTION

This Charter describes the roles and responsibilities for the NHLBI Gene and Cell Therapy Data and Safety Monitoring Board (DSMB).

The DSMB may wish to review this Charter at regular intervals to determine whether any changes are needed.

